5.3 Removal of Subjects from Treatment

The participation of a subject in the study or the administration of treatment may be terminated at any time for one of the following reasons:

- The subject desires to discontinue study treatment.
- The subject withdraws consent to participate in the study.
- The subject is unwilling or unable to comply with the safety procedures.
- The subject is discovered to be pregnant.
- The subject experiences a medical emergency that necessitates withdrawal.
- The subject is withdrawn at the discretion of the Investigator for medical reasons or non-compliance.
 - AST or ALT > 8 x ULN
 - ALT or AST > 3 x ULN AND total bilirubin > 2X ULN
 - AST or ALT > 3 x ULN AND patient has right upper quadrant pain or eosinophilia

- Uric acid >20mg/dL CrCl < 30

A subject whose treatment is terminated should remain in the study for appropriate follow up assessments whenever possible.

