
Individual Stopping Rule
	
A subject should be removed from favipiravir treatment if one of the following criteria is met:
 
 • AST or ALT > 8 x ULN • ALT or AST > 3 x ULN AND total bilirubin > 2X ULN • AST or ALT > 3 x ULN AND patient has right upper quadrant pain or eosinophilia

	
 • Uric acid >20mg/dL 
A subject whose treatment is terminated should remain in the study for appropriate follow up assessments.

Study Measurements: Efficacy, Safety and PK
	
Primary Measurement (Efficacy):
 
 1. Time to first of two negative tests based on nasal swab for RT-PCR taken daily from Day 1 to Day 10, and Days 14, 21, and 28. 
Secondary Measurements (Safety, Efficacy and PK):
 
 2. Oropharyngeal swab for nucleic acid (RT-PCR) taken Day 1, 5, 10, and 28. 3. Symptom improvement or worsening: Subjects will fill in a diary daily, recording the following symptoms: 
 a. Cough b. Sore throat c. Headache d. Nasal congestion e. Body aches and pains f. Fatigue g. Oral temperature taken after 4 pm and at least four hours after ingesting the most recent antipyretic (acetaminophen or NSAID) h. Dyspnea i. Shaking chills j. New loss of taste or smell k. GI symptoms including nausea, vomiting, and/or diarrhea l. Chest pain 4. Safety as assessed by: 
 a. Observed and reported adverse events b. Clinical laboratory evaluations of blood on Days 1, 5, 10, and 28 c. Physical Examination at screening (pre-dose Day 1), Days 10, and 28 d. Daily vital signs: pulse oximetry, heart rate, and temperature. 5. Optional Blood for determination of antibodies to SARS-CoV-2 will be obtained on Days 1 and 28. Collection of blood for antibodies is optional for sites. 6. Optional Blood for PK obtained pre-dose (within 30 minutes prior to dosing) and post-dose (45 to 75 minutes following dosing) on Days 1, 5 and 10. Collection of PK is optional for sites. 7. Optional Stool samples for determination of viral load in stool and microbiome characterization will be obtained in the following

	windows Day 1±5, 14±7, and 28±7. Collection of stool is optional for sites.
--	---

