3.2 Study Sites

This study is being supported by the Stanford Innovative Medicines Accelerator (IMA), Clinical Trials Research Unit (CTRU), and the Stanford Center for Clinical Research. This study may be performed at up to 5 sites nationally.

Each investigator or group of investigators at a clinical site must obtain Institutional Review Board (IRB) approval for this protocol and submit all required regulatory documents (including any protocol specific documents) to their respective IRB as required per institution. Sites can submit through a Stanford-designated central IRB for this trial. All subsequent mentions of IRB related activity in this document will reflect whichever choice they decide, be it local or central IRB.

Requirements for site selection and site registration: Sites will be evaluated by Stanford team and the main PI prior to selection or activation.

Stanford requires documentation that verifies IRB-approval for this protocol, informed consent documents, and associated documents prior to recruitment, screening, and enrollment of subjects, and any IRB-approvals for continuing review or amendments.

Please refer to the MOP for information on:

- Requesting and submitting regulatory documents
- Patient enrollment & randomization
- Randomization notification
- Requesting study drug
- Withdrawals
- Lost to follow-up
- Protocol deviations
- Data submissions

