5.2 Exclusion Criteria

All criteria must be confirmed as “NO”:

1. Subject has a concomitant bacterial respiratory infection, as defined by positive respiratory culture
2. Subject has a history of abnormalities of uric acid metabolism unless cleared
3. Subject has a history of hypersensitivity to an anti-viral nucleoside-analog drug targeting a viral RNA polymerase
4. Subject has any of the following abnormal laboratory test results at screening:
 - a. Platelet count $<100,000$ cells/mm³
 - b. Absolute lymphocyte count <500 cells/mm³

- c. Hemoglobin <11 g/dL for women and <12 g/dL for men
 - d. Serum creatinine concentration $\geq 1.5 \times$ ULN
 - e. Confirmed creatinine clearance (CrCl) < 50 mL/min by Cockcroft-Gault
 - f. Serum uric acid >20mg/dL
5. Subject is using adrenocorticosteroids (except topical or inhaled preparations or oral preparations equivalent to or less than 10 mg of oral prednisone) or immunosuppressive or immunomodulatory drugs (e.g., immunosuppressants, anticancer drugs, interleukins, interleukin antagonists or interleukin receptor blockers).

NOTE: Treatment of study participants following institutional COVID-19 treatment policies or guidelines, including the use of immunomodulatory medications, is permitted. This excludes treatment with agents that have the potential for direct antiviral activity, including convalescent plasma and NO, and co-enrolment into other clinical studies that evaluate investigational agents for COVID-19.

6. Subject has a serious chronic disease (e.g., human immunodeficiency virus [HIV], cancer requiring chemotherapy within the preceding 6 months, moderate or severe hepatic insufficiency and/or unstable renal, cardiac, pulmonary, neurologic, vascular, or endocrinologic disease states per investigator judgement).
7. Has previously received favipiravir within the past 30 days.
8. Has renal insufficiency requiring hemodialysis or continuous ambulatory peritoneal dialysis (CAPD).
9. Has liver impairment greater than Child-Pugh A. (NOTE: Child-Pugh A subjects will have the maintenance dose decreased to 800 mg BIID).
10. Has a history of alcohol or drug abuse in the previous 6 months.
11. Has a psychiatric disease that is not well controlled where controlled is defined as: stable on a regimen for more than one year.
12. Has taken another investigational drug within the past 30 days.
13. Is deemed by the Investigator to be ineligible for any reason.

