7.2 Day 1 (FIRST DOSE AND POST-DOSE)

NOTE: Day 1 is deemed to be the first 24 hours after enrollment into the study, with time 0 (time of first dose) occurring as quickly as possible after the subject's eligibility has been confirmed.

- Administer first dose (1800 mg favipiravir or placebo) at time 0.

Following First Dose:

- Monitor patient for 30 minutes after their first dose.
- Optional: Take a blood sample 45 to 75 minutes following the first dose for post-dose PK analysis

7.3 Days 5, 10, 28 (Follow-up) or Early Termination (Window of +1 or -1 day allowed on Days 5 and 28. Window of -1 allowed for Day 10.)

- Conduct and record the results of a Physical Exam (Day 5, 10, 28).
- Review and record concomitant medications (Note: if there have been changes in concomitant medications during the study, determine whether the change is due to an AE).
- Measure and record vital signs (BP, HR, Temp, Resp).
- Collect and record SPO2 by Finger Sensor
- Collect oropharyngeal swab for virologic testing (RT-PCR) and resistance analysis.
- Collect and record adverse events (see Section 8.4 for detailed instructions).
- Collect nasal swab for antigen testing and molecular viability testing (day 1, 5, 10)
- Collect blood samples for:
 - Hematology and clinical chemistry laboratory analyses (Day 5, 10, 28)
 - Urine for repeat pregnancy test (Day 5)
 - Optional: Antibodies to SARS-CoV-2. (28)
 - Optional: Biobanking (28)
 - Optional: Blood for PK and resistance analysis obtained pre-dose (within 30 minutes prior to dosing) and post-dose (45 to 75 minutes following dosing) (Days 5 and 10).
- Optional: Provide Zymo fecal stool collection kit: one on Day 1, two on Day 10, and 28.

- Optional: Collect stool samples on Day 5, 14, 28, and patient sends in sample at 4 months post enrollment date.

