8.4 Safety Assessments

Abnormal clinical laboratory values that are clinically significant and all reported adverse events will be graded according to the Common Terminology Criteria for Adverse Events (CTCAE) version 5.0.

Safety will be assessed by the collection of observed and reported adverse events, physical exams, vital signs and the following clinical laboratory tests:

- **Hematology**

Hemoglobin (Hgb)	Hematocrit (Hct)
Platelet count	Red blood cell count
White blood cell count with differential	

- **Chemistry**

Blood Urea Nitrogen (BUN)	Creatinine
Total bilirubin	Alkaline Phosphatase
Aspartate transaminase (AST)	Alanine transaminase (ALT)
Gamma-glutamyl transferase (GGT)	Albumin
Glucose	Bicarbonate
Total protein	Sodium
Phosphate	Chloride
Potassium	
Calcium	C-reactive protein
Urate	

NOTES:

- All clinical laboratory assessments listed above (hematology and chemistry) will be conducted at the Stanford University Medical Center clinical laboratory.
- If coagulation assays are ordered as part of the SOC, the results should be added to the EDC.

Including PK and Clinical Laboratory Testing, subjects will undergo up to 7 planned venipunctures during this study.

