8.6 Clinical Laboratory Abnormalities and Other Abnormal Assessments

Laboratory abnormalities are usually not recorded as AEs unless considered to be clinically significant by the site clinician. An abnormal laboratory result will be considered an AE if it induces clinical signs or symptoms, if the abnormality is of a degree that requires active management (e.g. discontinuation of the study drug, dose modification) or when the event is requiring treatment or other therapeutic intervention (e.g. iron supplements, blood transfusion, etc.).

The Investigator will evaluate the relationship of any significantly abnormal result to protocol treatment and clinical condition, if possible. All clinically significant abnormal laboratory results will be followed until they return to normal or become stabilized.

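### The individual stopping rule is stated inconsistently: the synopsis directs removal on four criteria and has no renal limit, while Section 5.3 adds CrCl < 30 under permissive wording

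*Combined protocol and SAP*

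**What the plan says.** The protocol states on-treatment stopping limits in two places.

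- **Synopsis, Individual Stopping Rule.** The lead-in is "A subject should be removed from favipiravir treatment if one of the following criteria is met". Four criteria follow: three hepatic and one for uric acid. There is no renal criterion.
- **Section 5.3, Removal of Subjects from Treatment.** The lead-in says that a subject's participation or "the administration of treatment may be terminated at any time for one of the following reasons". The list includes wish to stop, withdrawn consent, pregnancy, medical emergency, and withdrawal at the investigator's discretion. The same four laboratory or clinical criteria come after that last reason, and the final line reads "Uric acid >20mg/dL CrCl < 30".

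The other limits on creatinine or CrCl apply at screening only, for example "Confirmed creatinine clearance (CrCl) < 50 mL/min by Cockcroft-Gault" in Section 5.2. On-treatment laboratory work is scheduled in Section 7.3: "Hematology and clinical chemistry laboratory analyses (Day 5, 10, 28"). Section 3.2 sends sites to the MOP for several topics, withdrawals among them ("Please refer to the MOP for information on").

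**The concern.** A limit at which a subject stops study drug should appear once, or identically wherever it appears, and should say whether stopping is required. Here the lists differ by one item and the lead-ins differ in force. Both are current text, and nothing in the protocol reconciles them.

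What is at stake is consistent protection of participants across up to five sites. Section 2.3 names uric acid elevation as one of the two most common adverse events of the drug, and Section 2.7 says such elevations resolve when dosing stops. Whether stopping is directed or optional at the stated limit therefore bears on a known drug effect. For the renal limit, a subject whose CrCl is below 30 at the Day 5 visit meets a criterion that the sponsor wrote down, but no sentence directs the site to act on it.

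**Working it through.** No figure in the plan needs reproducing. The check compares the two texts and then gauges how far CrCl must fall.

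**Step 1. The two lists side by side.**

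| Criterion | Synopsis | Section 5.3 |
|---|---|---|
| 1. AST or ALT > 8 × ULN | should | may |
| 2. ALT or AST > 3 × ULN with total bilirubin > 2 × ULN | should | may |
| 3. AST or ALT > 3 × ULN with right upper quadrant pain or eosinophilia | should | may |
| 4. Uric acid > 20 mg/dL | should | may |
| 5. CrCl < 30 | absent | may |

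Four of the five criteria are directive in the synopsis and appear under permissive wording in Section 5.3. One of the five, CrCl < 30, is directive in neither.

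**Step 2. Can the texts be applied together?** Yes. The synopsis directs removal for criteria 1 to 4, and Section 5.3 names a further reason. On that reading only the force of criterion 5 is open. On Section 5.3 alone, the force of all five is open.

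**Step 3. Does another section settle it?** Sections 5.2, 8.4 and 8.6 do not. Section 5.2 governs entry. Section 8.4 lists the tests ("Safety will be assessed by the collection of observed and reported adverse events, physical exams, vital signs and the following clinical laboratory tests"). Section 8.6 says a laboratory result counts as an adverse event if, among other conditions, "the abnormality is of a degree that requires active management (e.g. discontinuation of the study drug, dose modification"). That classifies a result and does not order stopping.

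**Step 4. How far must CrCl fall?** At fixed age, weight and sex, Cockcroft-Gault CrCl is inversely proportional to serum creatinine. From a baseline b in mL/min, reaching 30 needs a fall of (b − 30)/b and a creatinine ratio of b/30. The value 50 is the entry limit in Section 5.2. The other baselines are assumptions, because the protocol gives no distribution.

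| Baseline b | Fall, (b − 30)/b | Creatinine ratio, b/30 |
|---|---|---|
| 50 (entry limit) | 20/50 = 40.0% | 1.67 |
| 70 (assumed) | 40/70 = 57.1% | 2.33 |
| 90 (assumed) | 60/90 = 66.7% | 3.00 |
| 120 (assumed) | 90/120 = 75.0% | 4.00 |

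A value below 30 needs more than the fall shown. The protocol gives no expected frequency for any of the five criteria.

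**Step 5. When could the rule act?** Dosing runs through Day 10. Of the post-baseline draws on Days 5, 10 and 28, only Day 5 falls well before dosing ends.

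**The case against.** The strongest reply is that the two texts do not conflict. Stopping satisfies both, and neither tells a site to continue. The Section 5.3 lead-in also covers withdrawn consent, where stopping is plainly not optional, so *may* there can mean only that termination can occur for these reasons. This has force. A reader might infer that the protocol makes the hepatic and uric acid limits optional, or that a site must choose which text governs. The documents support neither inference, because the synopsis wording stands and the texts can be combined. What survives is that the CrCl limit has no directive wording, and that a reader of Section 5.3 alone meets the limits beside an explicit reference to investigator discretion.

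Two other inferences also fail. The renal item shares a line with uric acid, which might suggest a combined criterion. The layout of the extracted text cannot settle that, and the point does not depend on it. The missing unit is not a substantive gap either, since Section 5.2 gives mL/min by Cockcroft-Gault.

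It is also fair to say that renal triggers will probably be few. Besides low CrCl, entry excludes creatinine at or above 1.5 × ULN, dialysis and unstable renal disease. The investigator can always withdraw a subject for medical reasons, and the MOP may hold a firm rule. These points limit the consequence. They do not make the two protocol statements agree.

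**Conclusion.** The point holds as a minor internal inconsistency, wrong as written, in a participant-safety threshold. Read together, the two texts leave four criteria with directive wording and one, CrCl < 30, with none. Read from Section 5.3 alone, all five could be taken as discretionary. The word *should* in the synopsis is directive but softer than *must*, so strictly neither text makes any limit mandatory.

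A reader might go further and infer that the trial has no binding stopping rule, or that its results are compromised. The first cannot be shown without the MOP. The second does not follow: Section 9.4 analyses efficacy in all randomized patients by assigned arm, Section 5.3 keeps subjects who stop treatment in follow-up whenever possible, and power and alpha do not depend on the rule.

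The wording comparison needs no assumption. The view that renal triggers will be few rests on the entry limit and on the assumed baselines above.

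**What to change.** Use one identical list in the synopsis and in Section 5.3, set apart from the general withdrawal reasons. Suggested text:

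> Study drug must be discontinued if any one of the following is met: (1) AST or ALT > 8 × ULN; (2) ALT or AST > 3 × ULN and total bilirubin > 2 × ULN; (3) AST or ALT > 3 × ULN and right upper quadrant pain or eosinophilia; (4) uric acid > 20 mg/dL; (5) CrCl < 30 mL/min (Cockcroft-Gault).

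Numbering makes the renal limit a separate item. *Study drug* suits a blinded trial better than naming favipiravir. If the MOP carries a withdrawal rule, align it with this list.

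The cost is protocol wording only. Creatinine, transaminases, bilirubin, urate and the white cell differential are already in the Section 8.4 panel, and the panel is already scheduled for Days 5 and 10, so no new test or visit is needed.

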5.4 Compensation

Compensation, if any, may be determined locally and in accordance with local IRB requirements and approval.

6 STUDY TREATMENT - FAVIPIRAVIR

6.1 Study Drug

Favipiravir will be provided in 200 mg tablet form to be stored at controlled room temperature (15°C to 30°C [59°F to 86°F]) and shielded from light. Matching placebo will be provided in tablet form to be stored at controlled room temperature (15°C to 30°C [59°F to 86°F]) and shielded from light.

Standard Dose

Subjects randomized to the favipiravir + SOC arm will be administered loading doses of 1800 mg BID (ideally 12 hours apart but 10-16 hours is allowed) on Day 1, and then maintenance dosing of 800 mg twice daily BID (Ideally 12 hours apart but 10- 16 hours is allowed) on Days 2-10 beginning 24 hours after the first dose. Day 1 is deemed to be the first 24 hours after enrollment into the study, with time 0 (time of first dose) occurring as soon as possible after the subject's eligibility has been confirmed.

An exception to the above maintenance dose will be made for those subjects entering the study with a Child-Pugh liver impairment of grade A who will receive favipiravir 600 mg BID on Days 2 through 10.

Subjects randomized to the placebo + SOC arm will be administered placebo BID (ideally 12 hours apart but 10-16 hours is allowed) on Day 1, and then maintenance dosing twice daily BID (Ideally 12 hours apart but 10- 16 hours is allowed) on Days 2-10 beginning 24 hours after the first dose. Day 1 is deemed to be the first 24 hours after enrollment into the study, with time 0 (time of first dose) occurring as soon as possible after the subject's eligibility has been confirmed.

6.2 Administration of Favipiravir or placebo

Favipiravir is provided as 200 mg tablets and dosed orally. Favipiravir is rapidly and completely absorbed after oral administration of the 200 mg immediate release tablets.

Subjects who vomit during or immediately after dosing, should not be re-dosed.

6.3 Outpatient Favipiravir Dosing

Subjects in the favipiravir + SOC arm, will be dispensed sufficient favipiravir to ensure continued dosing until their next study visit. Subjects in the placebo+ SOC arm, will be dispensed sufficient placebo to ensure continued dosing until their next study visit. Subjects in both arms will also be given a Diary Card to record the date and time they take their dose.

Subjects will also be instructed that if they miss a dose, they should follow the guidelines:

- 1) If more than 1/2 the time until their next dose has elapsed, they SHOULD NOT take the dose. They should just take the next dose at the normal scheduled time.
- 2) If less than 1/2 the time until their next dose has elapsed, they should take the missed dose immediately.
- 3) In both cases, they should then return to their regular dosing schedule.
- 4) The intention is to complete a 10-day course of medication. If, because of missed doses, there are leftover doses after completing their PM dose on Day 10, bring all additional doses to their next study visit.

6.4 Drug Accountability

The Investigator must maintain adequate records showing the receipt, dispensation, or other disposition of favipiravir including the date, quantity and identification of subjects (study ID) who received favipiravir. Drug supplies will be inventoried and accounted. Unused supplies of all favipiravir will be returned to the Sponsor (or designee) or destroyed on site in accordance with local procedures upon approval of the Sponsor.

6.5 Treatment Compliance

All doses of study drug will be administered by site staff while in the hospital. If the patient is discharged while still on drug, the pharmacy will provide bottles of favipiravir for outpatient use (Exact dispensing instructions for outpatients will be described in the pharmacy instructions). Assessment for compliance with each dose will be monitored and recorded in accordance with site standard operating procedures.

6.6 Treatment Precautions

An overdose is defined as any dose of study drug given to a subject or taken by a subject that exceeds the dose described in this document. In the event of an overdose, the subject should be treated symptomatically, and the Sponsor informed.

6.7 Prohibited Concomitant Therapy

The following may interact with favipiravir and risks and benefits should be carefully considered prior to treatment with the following:

- Any other anti-viral medication whether investigational or approved.
- Any drugs known to significantly inhibit AO activity (e.g., pyrazinamide, amitriptyline, chlorpromazine, clomipramine, clozapine, erythromycin, ketoconazole, nortriptyline, quetiapine, raloxifene, perphenazine, promethazine, propafenone, tamoxifen, thioridazine).
- Any drugs metabolized by the AO pathway (e.g., famciclovir, hydralazine, lamivudine, sulindac, zaleplon, ziprasidone).
- Drugs with possible drug-drug interactions (concomitant medications requiring particular attention – see the Investigator Brochure).

The following message appears on the daily questionnaire given to subjects with favipiravir to take at home:

Favipiravir can slightly increase the concentration of acetaminophen (Tylenol) in the blood. Do not take more than 3000 mg (do not forget to include any acetaminophen that could be in over-the-counter preparations) in a 24-hour period as long as you are taking favipiravir.

There are possible interactions of favipiravir with other drugs. During the time that you remain on favipiravir, do not take any medications or supplements that you were not taking before you started the trial, without getting approval first from the study doctor.

Favipiravir can cause you to be mildly sensitive to sunlight. Please avoid excessive exposure to sunlight or artificial ultraviolet light (tanning machines) while you are on favipiravir.

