2.2 Preclinical and In Vitro Experiences

Preclinical and animal studies indicate that favipiravir is effective against RNA viruses causing a variety of disorders.

Preclinical and animal studies show no direct suppression of white blood cell types or immunosuppression by favipiravir. This contrasts with strong immunosuppressive effects of ribavirin and other antiviral agents.

Genotoxicity studies indicate that favipiravir does not pose a clinical genotoxic risk, however, based on the results of embryo-fetal toxicity studies, favipiravir is not recommended for use in pregnant females, those who may become pregnant, or those who are nursing. A human testicular toxicity study was run to determine if there are effects on human spermatogenesis. No abnormality in testicular function tests was observed; however, this study was performed at doses less than those to be used in this study. Due to the effect on embryo-fetal development seen in animals, and the presence of favipiravir in semen for several days after the end of therapy, the recommendation is

for male and female contraception for seven days following the end of treatment, in the dose regimen for influenza. Details of the reproductive toxicity studies may be found in the Investigator’s Brochure.

Favipiravir is both metabolized by, and inhibits, aldehyde oxidase (AO). A potential interaction exists between favipiravir and drugs oxidatively metabolized by the AO pathway, where blood concentration of these drugs or favipiravir may be increased. Similarly, a potential interaction exists between favipiravir and drugs inhibiting AO activity, where blood concentration of favipiravir may be increased. Similarly, a potential interaction exists between favipiravir and drugs inhibiting AO activity, where blood concentration of favipiravir may be increased. Favipiravir should not be used with pyrazinamide.

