7.1 Day 1 (PRE-DOSE)

- Obtain informed consent.
- Verify eligibility per the inclusion and exclusion criteria. (See Sections 5.1 and 5.2)
 - Review and record medical history, including tobacco use, to ensure there are no exclusionary illnesses.
 - Review and record concomitant medications for possible prohibited medications. (See Section 6.7)
- If subject is female of child-bearing potential and meets inclusion criteria 11.c, obtain urine pregnancy test and proceed if result is negative.
- Measure and record vital signs (BP, HR, Temp, Resp).
- Collect and record SPO2 by Finger Sensor
- Perform Physical exam (may be done by the Principal Investigator or their designee)
- Complete baseline symptom survey to establish severity of symptoms (if present)
- Collect oropharyngeal swab for virologic testing (RT-PCR) and resistance analysis.
- Collect two nasal swabs for antigen testing and molecular viability testing.
- Collect blood samples for
 - Uric acid
 - CRP
 - Hematology and clinical chemistry laboratory analyses (samples collected within 48 hours of enrollment are acceptable):
 - Resistance analysis
 - Optional: Antibodies to SARS-CoV-2.
 - Optional: Biobanking
 - Optional: Pre-dose PK

- Perform subject randomization (via EDC) to establish treatment arm (favipiravir + SOC or placebo + SOC).
- Explain in home procedures for the study (self-sampling of nasal swabs, temperature, SPO2, completing the daily questionnaire and the optional collection of stool sample).
- Provide supplies to research subject and review the calendar of return visits.
- Optional: Explain that stool sample from first bowel movement after enrollment should be collected in Zymo fecal tube and brought back to Day 5 follow-up visit. If the first bowel movement sample cannot be collected, it is permitted to collect a subsequent bowel movement sample.

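### Section 6.7, the list sites use on Day 1 to screen for prohibited medications, only asks them to weigh pyrazinamide, which section 2.2 rules out

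*Combined protocol and SAP*

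**What the plan says.** Section 2.2 explains that favipiravir is both metabolized by aldehyde oxidase (AO) and an inhibitor of it. It warns of an interaction with "drugs inhibiting AO activity, where blood concentration of favipiravir may be increased", and ends the paragraph with a flat statement: "Favipiravir should not be used with pyrazinamide".

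Section 6.7 carries the word Prohibited in its heading. Its lead-in says only that the listed drugs may interact with favipiravir and that "risks and benefits should be carefully considered prior to treatment with the following". Four groups follow: other antivirals, AO inhibitors, AO substrates, and drugs flagged in the Investigator Brochure. Pyrazinamide is the first example in the second group: "Any drugs known to significantly inhibit AO activity (e.g., pyrazinamide".

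Section 7.1 makes section 6.7 part of the Day 1 eligibility check: "Review and record concomitant medications for possible prohibited medications. (See Section 6.7". The same step requires a check against the criteria in sections 5.1 and 5.2. It does not refer to section 2.2.

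A note under criterion 5 of section 5.2, repeated in the synopsis, permits institutional COVID-19 treatment except agents with potential direct antiviral activity and co-enrolment in other COVID-19 treatment studies.

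**The concern.** The one clear bar on pyrazinamide sits in a background section to which the screening procedure does not point. The section it does point to asks for judgement. A participant already taking pyrazinamide could pass the Day 1 review as written and receive favipiravir together with a drug that the protocol itself lists as an AO inhibitor, and section 2.2 says such inhibitors may raise favipiravir concentration. What is at stake is participant safety.

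Consistent conduct is at stake too. A site that goes by the heading of section 6.7 and by section 7.1 might turn away users of every drug on the list. A site that goes by the lead-in need turn away none. With up to 5 sites, the same patient could get different answers.

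**Working it through.** No formula applies and the plan gives no figure to reproduce. The check sets the texts side by side.

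1. **Where the drug is named.** In two places only: section 2.2 (background) and section 6.7 (used for screening through section 7.1).

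2. **What each text allows.**

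| Site's decision on a pyrazinamide user | Consistent with 2.2? | Consistent with 6.7? |
|---|---|---|
| Always declines | Yes | Yes |
| Weighs risks and benefits, then doses | No | Yes |

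The second row is the defect: section 6.7 permits what section 2.2 says should not be done. The first row shows that the two can be followed together.

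3. **Whether the exclusion criteria close the gap.** Section 5.2 has 13 criteria, and 0 name pyrazinamide or AO inhibitors. The synopsis numbers its exclusions 11 to 22, so 22 − 11 + 1 = 12 items, and 0 name them. Three criteria in section 5.2 restrict a current or recent medicine: criterion 5 (corticosteroids, immunosuppressive and immunomodulatory drugs), criterion 7 (favipiravir) and criterion 12 (investigational drugs). Criterion 6 also mentions chemotherapy. None is directed at pyrazinamide. Criterion 13 lets the investigator exclude anyone, but that is discretion and not a rule.

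4. **Whether anything closes it during dosing.** The participant message in section 6.7 covers only drugs "that you were not taking before you started the trial, without getting approval first from the study doctor". It misses existing use, and for a new drug it hands the decision to the study doctor, whose list is section 6.7. The medication review in section 7.3 asks, "if there have been changes in concomitant medications during the study, determine whether the change is due to an AE", and does not refer to section 6.7.

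5. **How many listed drugs are affected.** Section 6.7 names 15 AO inhibitors and 6 AO substrates: 15 + 6 = 21. One of the 21, pyrazinamide, is ruled out by name elsewhere. For the other 20 (14 inhibitors and 6 substrates) no other section sets a stricter rule by name, so the risk-benefit wording conflicts with nothing.

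6. **Antivirals.** Section 6.7 lists any other antiviral as something to weigh, which is looser than the section 5.2 note. But section 7.1 requires the section 5.2 check in the same step, so the note stays in force, and criterion 12 bars investigational drugs taken in the 30 days before entry. The looser wording is a duplicate rule that should be aligned. It does not open a gap.

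**The case against.** The strongest reply is that a sensible site would read the heading of section 6.7, the wording of section 7.1 and the statement in section 2.2 together as a bar. Section 6.7 does not authorise pyrazinamide; it gives an instruction for a class and names the drug as an example. Part of this stands. A reader might infer that the protocol contains two rules that cannot both be followed, and the documents do not support that, because a site that always declines obeys both. What remains is that the instruction under the heading is weaker than the heading, and nothing in the screening procedure sends a site to section 2.2.

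A second reply is that other documents may state the bar: the Investigator Brochure (cited in section 6.7), the MOP (section 3.2) or the pharmacy instructions (section 6.5). They may, but they cannot be seen here and should not be assumed to repair the protocol text.

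A third is that chemistry is measured on Days 1, 5, 10 and 28, with stopping rules for liver tests and uric acid in section 5.3. These may limit harm once exposure has occurred. They do not prevent co-administration.

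A reader might also infer that section 6.7 lets other antivirals into the trial and so threatens the shedding endpoint. The documents do not support that either, since the section 5.2 note and criterion 12 still govern. Nor should much be made of the follow-up medication reviews: dosing ends on Day 10, so a check against section 6.7 on Day 28 could not prevent co-administration.

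**Conclusion.** The point holds in a narrow form. For pyrazinamide, the operative screening rule in section 6.7 is looser than the protocol's own statement in section 2.2, and no exclusion criterion makes up the difference. The text should be corrected, but the matter is minor.

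Its size is 1 of 21 named drugs. The documents give no figure for pyrazinamide use or for the resulting change in favipiravir concentration, so no effect size is claimed, and no effect on the shedding endpoint or any analysis. Pyrazinamide is singled out because it is the only listed drug that the protocol rules out by name; nothing here says its interaction is larger than that of the other inhibitors.

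The conclusion assumes that the statement in section 2.2 reflects the sponsor's intent, and that a site may act on the text of section 6.7 without consulting section 2.2.

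**What to change.** - In section 6.7, state that pyrazinamide must not be used from screening to the last dose of study drug. Cross-refer to this from section 5.2 so that a current user is excluded.
- Keep the risk-benefit wording for the other AO inhibitors, the AO substrates and the Investigator Brochure drugs, and label that list as use with caution.
- For antivirals, add to section 6.7 only that the section 5.2 note on agents with potential direct antiviral activity governs.
- Optionally, refer the medication review at the on-treatment visits (Days 5 and 10) in section 7.3 to section 6.7.

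The cost is a few words of protocol text and the loss of any pyrazinamide user from enrolment. No new visit, data item or analysis is needed.
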